1.2 Rationale for Selection of Study Population

This protocol is designed to identify participants who have persistent peanut allergy. By specifically targeting participants who are at the highest risk for life-long peanut sensitivity, we anticipate that we might maximize the benefits of desensitization and/or clinical tolerance induction. By including in our protocol design a post-therapy challenge after a significant allergen avoidance period, we will better distinguish true tolerance from desensitization and some of the immune changes associated with varying clinical outcomes. A blinded placebo control group is included, to control for possible changes in clinical sensitivity over time independent of therapy. The selection of older adolescents and adults will also allow us to better study immunological changes using assays that require blood volumes that would not be feasible to obtain in a younger population.

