2.2 Secondary Objective(s)

2.2.1 Clinical:

- To evaluate whether PN OIT induces increased tolerance, defined as a statistically significant increase in the median eliciting dose (ED) from DBPCFC1 to DBPCFC3.
- To evaluate whether PN OIT induces clinical desensitization, defined as 1) a median 10-fold or greater increase in ED from DBPCFC1 to DBPCFC2; 2) a statistically significant higher median ED at DBPCFC2 between active and control treatment; and 3) a significantly lower frequency of accidental ingestion reactions in active versus control treatment.
- To evaluate the safety of PN OIT.

2.2.2 Mechanistic:

- To determine whether PN OIT induces a statistically significant increase in the TCR clonal diversity of Treg
 populations during active treatment among participants who achieve increased clinical tolerance (Tolerance
 and Partial Tolerance Groups as defined in clinical endpoints) versus the Treatment Failure Group.
- To determine whether PN OIT suppresses mast cells by inducing a significant suppression of the median ED on end-point dilution skin testing in actively treated participants by the end of maintenance therapy.
- To determine whether PN OIT suppresses basophils as defined by a 10-fold suppression of peanut-specific basophil ED in actively treated participants by end of maintenance.
- To determine whether either mast cell or basophil suppression at the end of maintenance therapy is significantly associated with clinical outcomes following avoidance.

2.2.3 Exploratory:

- To describe the gene expression profiles and clonal diversity of regulatory and effector T cell subsets before
 and after OIT to better understand the phenotype and ontogeny of these subsets and potentially discover
 new therapeutic pathways.
- To engineer human MHC class II tetramers on common HLA backgrounds and map T cell epitopes of the dominant peanut allergens for use in validating earlier findings and for future studies of peanut-specific immune responses in humans.
- To determine whether microbial dysbiosis is associated with the development of desensitization, oral tolerance, or persistent gastrointestinal adverse events while on oral immunotherapy.

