3.1.2 Secondary Endpoint(s)

Secondary endpoints are:

Clinical:

- Tolerance:
 - The change in median eliciting dose (ED) from DBPCFC1 to DBPCFC3.
- Desensitization:
 - The change in median eliciting dose (ED) from DBPCFC1 to DBPCFC2.
 - The frequency of accidental ingestion reactions in active versus control treatment.
- Safety:
 - Anaphylaxis requiring more than 1 administration of epinephrine; or hospitalization.
 - Death as a result of the investigational product.
 - The rate of reported adverse advents due to accidental ingestions in the active versus placebo groups.

Mechanistic:

- The change in the TCR clonal diversity of in vitro allergen-expanded Treg cells and induced Treg cells measured by TCRβ CDR3 sequence clonotyping of sorted cells during active treatment among participants who achieve increased clinical tolerance (Tolerance and Partial Tolerance Groups as defined in clinical endpoints) versus the Treatment Failure Group.
- The change in ED of end-point dilution skin testing between actively treated and placebo treated participants following maintenance therapy.
- The change in ED of end-point dilution skin testing among actively treated participants following maintenance therapy and avoidance between clinical outcome groups.

- The change in peanut-specific basophil ED in actively treated participants at the end of maintenance and the end of avoidance between clinical outcome groups.
- The change in peanut allergen-specific IgG4 in actively treated participants by the end of maintenance between clinical outcome groups.
- The change in Ara h 2 specific surface and secreting B cells between baseline (measured after 12 weeks
 of treatment) and the end of maintenance.
- Statistically significant gene expression changes by transcriptional profiling of regulatory and effector T cell participants before and after OIT between clinical outcome groups.

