7.4.4 Maintenance Visits (Days 350-434)

Maintenance visits will occur on the MGH CRC monthly during the 12 weeks of maintenance therapy. Each visit will involve a medical history and physical examination. The medical history will consist of a structured interval clinical history and review of systems concerning any types of allergic symptoms related to their food allergy, atopic dermatitis or asthma. The participants and/or their parents will record any known accidental ingestion that occurs during the study. The physical exam will include vital signs, and spirometry. A negative urine pregnancy test will be documented for female participants of child-bearing potential; if the test is positive, the visit will be cancelled and if pregnancy is confirmed, the subject will be withdrawn from the study.

Blood will be collected and skin prick testing will be performed at three follow-up visits for research laboratory studies at baseline, on maintenance therapy (after 12 weeks at 4000 mg of peanut protein or maximum tolerated) prior to DBPCFC2, and prior to DBPCFC3 (12 weeks post avoidance). An additional blood draw will occur during build up (12 weeks after beginning treatment). Blood will be drawn by trained study staff or Clinical Research nurses. Urine will be collected from female participants for a Human Chorionic Gonadotropin (HCG)-based pregnancy test at all follow up visits throughout the study.

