16 APPENDICES

16.1 Schedule of Events

Time Points (day)	-7	0	28	42	43–350	350-434	434	434–518	518
Visit	0	-	2	င	4 to 25	26 to 28	28	29 to 31	31
	(Screening)	(Baseline)	(DBPCFC1)	(Modified Rush)	(Build Up)	(Maintenance)	(DBPCFC2)	(Avoidance)	(DBPCFC3)
GENERAL ASSESSMENTS									
Informed consent	×								
Medical history	×	×	×	×	×	×	×	×	×
Verify eligibility	×								
Randomization				×					
Physical exam	×	×	×	×	×	×	×	×	×
Pulmonary Function Testing	×	×	×	×	×	×	×	×	×
OIT Dosing				×	×	×			
DBPCFC			×				×		×
AE assessment		×	×	×	×	×	×	×	×
Nutrition Consult		×					×		
Skin prick test	×								
Titration skin test		×				X (Visit 27)		×	
LAB ASSESSMENTS									
Urine pregnancy test	×	×	×	×	×	×	×	×	×
Mechanistic T cell		×				X (Visit 27)		×	
Basophil Activation		×				X (Visit 27)		×	
Mechanistic B cell		×			X (Visit 10)	×			
slgE, lgG4	×					X (Day 448)		×	
Stool Collection (optional)		×			X (Every 3 months)	X (Every 6-12 months)		X (Every 6-12 months)	

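### The basophil objective judges OIT by a 10-fold change in the active arm alone, and no listed endpoint compares basophil ED with placebo

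*Combined protocol and SAP*

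**What the plan says.** **Basophils.** The mechanistic objective in section 2.2.2 is to determine whether OIT "suppresses basophils as defined by a 10-fold suppression of peanut-specific basophil ED in actively treated participants by end of maintenance". The only basophil endpoint in section 3.1.2, repeated in the synopsis, is "The change in peanut-specific basophil ED in actively treated participants at the end of maintenance and the end of avoidance between clinical outcome groups".

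**Mast cells.** The companion objective in 2.2.2 looks for a "significant suppression of the median ED on end-point dilution skin testing in actively treated participants by the end of maintenance therapy". Here section 3.1.2 does list a randomised comparison: "The change in ED of end-point dilution skin testing between actively treated and placebo treated participants following maintenance therapy".

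**Placebo arm.** Section 1.2 gives its purpose: "A blinded placebo control group is included, to control for possible changes in clinical sensitivity over time independent of therapy". Section 9.1 says it will serve mainly to compare adverse events, and adds an intention-to-treat analysis of the Treg outcome. Section 9.2.4 covers the primary endpoint only. No analysis is written for skin-test or basophil ED.

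**Sampling.** Section 7.4.4 states: "Blood will be collected and skin prick testing will be performed at three follow-up visits for research laboratory studies at baseline, on maintenance therapy". The Schedule of Events (16.1) has one row for "Basophil Activation" and one for the titration skin test, each marked at baseline, Visit 27 and avoidance, with no split by arm. Section 7.1 places unblinding after DBPCFC2.

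**The concern.** The basophil objective is a causal statement about OIT, but its criterion is a before/after change in treated participants. That change is the OIT effect plus whatever else moved between Day 0 and the end of maintenance, which falls at about Day 434, some 14 months later. Changes in assay performance or reagents, or in the participants' own sensitivity, would affect both arms alike. The active arm alone cannot separate them from the effect of OIT.

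The outcome-group comparison in 3.1.2 does not fill the gap. It serves the last objective in 2.2.2, whether suppression is associated with clinical outcome. It does not show whether OIT caused the suppression.

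At stake is a mechanistic conclusion. A shared shift towards lower reactivity would inflate the reported suppression, and a shift the other way could hide a real effect.

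**Working it through.** **1. Objectives and endpoints side by side**

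| Measure | Criterion in 2.2.2 | Endpoints in 3.1.2 | Active v placebo listed? |
|---|---|---|---|
| Basophil ED | 10-fold change, active arm | Outcome groups within active arm | No |
| Skin-test ED | Significant change in median, active arm | Active v placebo; also outcome groups within active arm | Yes |
| Food-challenge ED, desensitization (2.2.1) | 10-fold median rise and a significantly higher median than control | Change in median ED, DBPCFC1 to DBPCFC2 | Yes, in the objective |

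The desensitization objective already pairs a 10-fold rule with a control contrast. The basophil objective keeps only the first half.

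**2. Are placebo samples available?** The schedule has Visit 27 within maintenance and DBPCFC2 at Visit 28, and unblinding follows DBPCFC2. Section 7.7.6 assigns 5 ml of each large draw to basophil activation without limiting it to the active arm. Blinded placebo samples should therefore exist at Day 0 and Visit 27. This is inferred from a schedule not split by arm; no sentence says it outright. After DBPCFC2 placebo participants may go on to open-label OIT, so the contrast is sound only up to Visit 27.

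**3. The plan's own figure.** No power is given for these measures. The nearest stated figure is Table 15.6: 8 v 14, difference 1.5 SD, two-sided alpha 0.05, power 0.90. The noncentral-t calculation gives 0.896, so the same formula is used in step 5.

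**4. Effect of a shared shift (illustrative).** Write the log10 change in the active arm as shared shift + OIT effect + error. Assume normal errors, read the 10-fold rule as a median change of at least 1 log10 towards lower reactivity, and take 22 to 30 active participants with data. The plan states neither the SD nor the shift.

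- Size: with a true effect of 1 log10 and a shared shift of 0.3 log10 (two-fold), the active arm shows 10^1.3, about 20-fold, or 10^0.7, about 5-fold.
- Chance of meeting the rule, true effect exactly 10-fold, 30 active, by simulation: at SD 0.7 it is 50% with no shift, 97% with +0.3 and 3% with −0.3. At SD 1.0 it is 50%, 91% and 9%. An effect exactly on the threshold is the most sensitive case.
- Chance of meeting the rule with no OIT effect, 22 to 30 active, SD 0.5 to 1.5: at most 10% for a shared shift of 0.5 log10 or less, 1% to 26% at 0.75 log10, and about 50% only if the shift is itself 10-fold.

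**5. What the randomised contrast would deliver.** Unadjusted 95% half-width = t × SD × √(1/n₁ + 1/n₂). For 30 v 10 at SD 0.7 this is 2.024 × 0.7 × √(1/30 + 1/10) = 0.52 log10. The one-sample half-width for 30 active is 2.045 × 0.7 / √30 = 0.26 log10. Power for a true 10-fold difference:

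| SD of log10 change | 30 v 10 | 22 v 10 |
|---|---|---|
| 0.5 | >0.99 | >0.99 |
| 0.7 | 0.97 | 0.95 |
| 1.0 | 0.76 | 0.72 |
| 1.5 | 0.43 | 0.39 |

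**The case against.** The strongest reply is that the basophil criterion is demanding. A reader might infer that the plan credits OIT with any before/after change. It does not: basophils need a 10-fold change and mast cells a significant one. Step 4 shows that moderate shared drift alone seldom produces 10-fold. That stands, and it limits the harm mainly to the size of the effect.

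A reader might also infer that the mast-cell question lacks a control. It does not, because 3.1.2 lists the active versus placebo skin-test endpoint. The objective and endpoint are worded differently, but no comparison is missing. High false-positive rates can be computed for a one-sample skin-test analysis under shared drift, but no section specifies such a test.

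Regression to the mean is tempting as a mechanism, since entry requires a reaction at DBPCFC1. That selection is on the food challenge at Day 28. Basophil and titration skin-test baselines are taken at Day 0, and participants are not selected on either, so the argument is weak here. Nor do the documents report any assay drift.

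Finally, these are secondary mechanistic measures in a phase I/II study with about 10 placebo participants, and the contrast will be imprecise if the assay is variable. That is true, but an imprecise randomised estimate still separates OIT from time, which the active-arm change cannot do.

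**Conclusion.** The point holds for basophils. As written, the plan would conclude that OIT suppresses basophils without comparing the randomised arms, although the control samples appear to be collected. The likely harm is a mis-stated effect: about 20-fold or 5-fold in place of 10-fold under an assumed two-fold shared shift. A false claim from drift alone is unlikely unless drift is itself close to 10-fold. For mast cells only a mismatch between objective and endpoint remains.

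These sizes rest on assumed SDs and shifts, normal log10 changes and reading the 10-fold rule as a median. The availability of placebo samples rests on the unsplit schedule. The gap in the endpoint list depends on none of the numerical assumptions. The change is worth making because it is cheap and follows the standard that section 2.2.1 already sets for desensitization.

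**What to change.** 1. Add to section 3.1.2 (and the synopsis) an active versus placebo comparison of change in log10 basophil ED from Day 0 to the end of maintenance (Visit 27), adjusted for baseline log10 ED, with a 95% CI.
2. In section 2.2.2, base the basophil conclusion on that contrast and report the 10-fold benchmark alongside it.
3. For mast cells, reword the 2.2.2 objective to match the existing active versus placebo skin-test endpoint. Use a rank-based or ordinal analysis: section 7.7.4 uses full-strength extract and four 10-fold dilutions, so ED can take only a few values.
4. Confirm in the protocol that placebo participants give both samples, and report by arm how many have them.
5. Leave the outcome-group comparisons within the active arm as they are.

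The cost is wording and one endpoint line, with no new visits, samples or participants. The price is precision: at an assumed SD of 0.7 log10 the half-width is about 0.52 log10 for 30 v 10, against 0.26 for the active arm alone.

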3 STUDY DESIGN

This is a phase I/II double-blind placebo-controlled interventional study of peanut allergen oral immunotherapy (OIT) for adolescents and adults (7 to 55 years of age) with IgE-mediated allergy to peanut (evidence of sensitization and demonstrated clinical reactivity). The major objective of this study is to provide additional safety and mechanistic data on OIT for people with IgE-mediated peanut allergy.

There will be 3:1 active to placebo randomization. The treatment substance is peanut flour. The placebo is roasted oat flour. An schematic of the design is presented in Figure 15.1. See Appendix 16.1 for schedule of study events.

Clinical assessments will be made by double-blind placebo-controlled food challenge at baseline (DBPCFC1), after 12 weeks of maintenance therapy (DBPCFC2) and then after an additional 12 weeks off therapy while strictly avoiding dietary peanut protein (DBPCFC3). Participants who do not react at \geq 443 mg of peanut protein (cumulative) during DBPCFC1 will be excluded from the study.

18 of 68

AADCRC Protocol 2012P002153

3.1 Study Endpoints

3.1.1 Primary Endpoint(s)

The difference in the proportion of induced Treg cells (CD45RA- CD25++ FoxP3++ of CD4+ T cells) from baseline to the end of maintenance therapy.

CONFIDENTIAL

Clinical outcomes will be defined as follows:

- Treatment Failure: Failure to achieve the minimum maintenance dose (600 mg) of peanut protein by 12 months, or an ED <1443 mg at DBPCFC2, or ED at DBPCFC3 <443 mg OR <10-fold more than at DBPCFC1.
- Partial Tolerance: ED at DBPCFC3 <4430 mg but ≥430 mg AND >10-fold more than at DBPCFC1.
- Tolerance: Ingestion of 4430 mg of peanut protein at DBPCFC3 without symptoms.

3.1.2 Secondary Endpoint(s)

Secondary endpoints are:

Clinical:

- Tolerance:
 - The change in median eliciting dose (ED) from DBPCFC1 to DBPCFC3.
- Desensitization:
 - The change in median eliciting dose (ED) from DBPCFC1 to DBPCFC2.
 - The frequency of accidental ingestion reactions in active versus control treatment.
- Safety:
 - Anaphylaxis requiring more than 1 administration of epinephrine; or hospitalization.
 - Death as a result of the investigational product.
 - The rate of reported adverse advents due to accidental ingestions in the active versus placebo groups.

Mechanistic:

- The change in the TCR clonal diversity of in vitro allergen-expanded Treg cells and induced Treg cells measured by TCRβ CDR3 sequence clonotyping of sorted cells during active treatment among participants who achieve increased clinical tolerance (Tolerance and Partial Tolerance Groups as defined in clinical endpoints) versus the Treatment Failure Group.
- The change in ED of end-point dilution skin testing between actively treated and placebo treated participants following maintenance therapy.
- The change in ED of end-point dilution skin testing among actively treated participants following maintenance therapy and avoidance between clinical outcome groups.

- The change in peanut-specific basophil ED in actively treated participants at the end of maintenance and the end of avoidance between clinical outcome groups.
- The change in peanut allergen-specific IgG4 in actively treated participants by the end of maintenance between clinical outcome groups.
- The change in Ara h 2 specific surface and secreting B cells between baseline (measured after 12 weeks
 of treatment) and the end of maintenance.
- Statistically significant gene expression changes by transcriptional profiling of regulatory and effector T cell participants before and after OIT between clinical outcome groups.

3.2 Study Completion

This study will be considered "completed" when the primary and secondary objectives have been met. This includes the analysis of all the data required to meet the chosen objectives.

After the study is completed, the Principal Investigator or Data Center will compile a final study report as per ICH E6 and 21CFR312. The study report will be submitted to the local IRB, NIAID, ISM and the FDA.

4 SELECTION AND WITHDRAWAL OF PARTICIPANTS

4.1 Inclusion Criteria

Individuals who meet all of the following criteria are eligible for enrollment as study participants:

- Diagnosis of peanut allergy by medical history
- Evidence of peanut-specific IgE by either: positive skin prick test to peanut (reaction wheal at least 5 mm larger than saline control) or serum peanut-specific IgE ≥5 kU/L at screening visit.
- Ara h 2 specific IgE >0.35 kU/L at screening visit.
- Who are willing to sign informed consent or whose parent or legal guardian is willing to sign the consent form (age appropriate)
- Who are willing to sign the assent form, if age appropriate
- Males and females of all ethnic/racial groups aged 7-55 years old who are otherwise healthy.
- React to ≤443 mg of peanut protein during DBPCFC1

4.2 Exclusion Criteria

Individuals who meet any of these criteria are not eligible for enrollment as study participants:

- History of severe anaphylaxis as defined by hypoxia (cyanosis or SpO2 <92% during reaction), documented
 hypotension (documented systolic BP >30% below predicted normal for sex, height, weight or from known
 baseline), neurological compromise (confusion, loss of consciousness), or incontinence.
- Severe or Moderate asthma as defined using the severity criteria of the current NHBLI Guidelines for the Diagnosis and Management of Asthma (http://www.nhlbi.nih.gov/guidelines/asthma/).

- Poorly-controlled asthma as defined by FEV1 <80% or any of the following symptoms: nighttime awakening >2 days/week or rescue medication use >2 days / week.
- Diagnosis of other severe or complicating medical problems, including autoimmune or chronic immune inflammatory conditions or gastrointestinal inflammatory conditions, including Celiac Disease, Inflammatory Bowel Disease and Eosinophilic Gastrointestinal Disorders
- Inability to cooperate with and/or perform oral food challenge procedures.
- Primary Immune Deficiency
- Allergy to oat confirmed by skin prick testing and history
- Current use of beta blockers, angiotensin converting enzyme inhibitors, or monoamine oxidase inhibitors
- Women of childbearing potential who are pregnant, planning to become pregnant, or breastfeeding
- Hematocrit < 0.36 for adult females or < 0.38 for adult males
- Weight <23 kg
- Use within the past 6 months of other systemic immunomodulatory treatments including allergen immunotherapy, or use of biologics with an immune target, including omalizumab.
- Past or current medical problems or findings from physical examination or laboratory testing that are not listed above, which, in the opinion of the investigator, may pose additional risks from participation in the study, may interfere with the participant's ability to comply with study requirements or that may impact the quality or interpretation of the data obtained from the study may also exclude a participant from the study.

4.3 Participant Withdrawal Criteria

Participants may be terminated early from the study for the following reasons:

- The participant elects to withdraw consent from all future study activities, including follow-up.
- The participant is "lost to follow-up" (i.e., no further follow-up is possible because attempts to reestablish contact with the participant have failed).
- The participant dies.
- The participant develops a medical condition or is started on new medication(s) not previously mentioned in the list of prohibited medications that, in the opinion of the investigator, may pose additional risks from participation in the study, may interfere with the participant's ability to comply with study requirements or that may impact the quality of the data obtained from the study.
- The participant meets any of the individual stopping rules as delineated in section 8.
- Dose adjustment required more than twice due to missed at-home dosing.
- Rescheduling of two consecutive, or more than four total dose escalation visits.

Participants with early termination from this study will not be replaced.

5 INVESTIGATIONAL PRODUCT(S) / INTERVENTION MATERIAL(S), OTHER STUDY PRODUCTS (CONTROLS/PLACEBOS)

